8. STUDY TREATMENTS

8.1 Allocation to Treatment

Each subject will be assigned a unique identification number upon screening. Subjects who complete the study screening assessments and meet all the eligibility criteria will be scheduled to enter the study and receive study treatment.

8.2 Blinding

None; this is an open-label study.

8.3 Treatments Administered

Sterile solutions of APL-2 up to 40 mg/mL in acetate-buffered mannitol administered by Subcutaneous infusion.

8.3.1 Drug supplies

8.3.1.1 Identity of Investigational Products

APL-2 will be supplied as a sterile solution of APL-2 in acetate-buffered mannitol at concentrations of up to 40 mg/mL, supplied in stoppered glass vials.

8.3.1.2 Study Supplies

The Sponsor will supply sufficient quantities of APL-2 drug product to allow completion of this study. The lot numbers, manufacture dates, and expiration dates of the drugs supplied will be recorded in the final report. The Sponsor will also supply needles, syringes, and ambulatory syringe infusion pumps as required. Refer to the Study Operations Manual for further information.

APL-2 acetate-buffered mannitol solution should be stored at 2-8°C. A pharmacist or appropriately qualified designated person will be responsible for storing the APL-2 appropriately; dispensing the vials of APL-2 to the subject, study nurse, or other study personnel, and for maintaining accountability records.

8.3.1.3 Accountability

Records will be made of the receipt and dispensing of APL-2 for administration both on and off-site.

At the conclusion of the study, any unused investigational product will either be destroyed at the investigator site or be returned to the Sponsor or designee for destruction, and destruction will be documented appropriately. If no supplies remain, this fact will be documented appropriately.

8.3.2 Planned Dose Levels and Dosing Schedule

Starting on Day 1 (Visit 3), subjects will receive SC APL-2 daily for up to 364 days.

Planned doses will be as follows:

Cohort	Planned dosing schedule
Single cohort	270 mg/day (up to 360 mg/day from Day 29) from Day 1 to Day 364*

* The dose may be increased up to 360 mg/day during Part 2A if the clinical response is sub-optimal. The volume to be administered will depend on the final concentration provided and will be administered as a SC infusion.

The dose for this study was determined based on safety, PK, and PD data from the ongoing studies in PNH patients.

Intra-subject dose escalations will be agreed by the Investigator and Sponsor and will be implemented on an individual subject basis and not necessarily applied across all subjects in the cohort. The dose for an individual subject will not exceed 360 mg/day (estimated to reach approximately 85 % of the C_{max} of the NOAEL observed in monkeys) without a protocol amendment.

8.3.3 Drug Administration

All doses will be administered as SC infusions.

The preferred site of injection will be the abdomen; however, if a subject does not tolerate administration into the abdomen alternative sites may be selected e.g. thigh or upper arm. Subjects will self-administer the SC infusions after receiving appropriate training by a research nurse or other study personnel. The injections will be administered at the clinic on those days when a clinic visit occurs and at an off-site location convenient to the subject on all other days.

Doses will be administered while subjects are seated.

Dosing records will be maintained at the clinical site and available for review by the sponsor.

8.4 Concomitant Medications

8.4.1 Prophylactic antibiotics

Prophylactic antibiotic therapy will be prescribed to all subjects to minimize potential infection risk. Prophylactic antibiotics will be initiated on day 1 following administration of APL-2 dosing and continue until 2 weeks after the last dose.

8.4.1.1 Primary prophylactic antibiotic Day 1-14

- Ciprofloxacin 500 mg twice daily, initial administration on Day 1 will take place at the initial APL-2 dosing, following ECG collection postdose.

8.4.1.2 Primary prophylactic antibiotic Day 15 onwards

- Penicillin V 500 mg twice daily

Serious and occasionally fatal hypersensitivity (anaphylactic) reactions have been reported in patients on beta-lactam antibiotic (e.g. penicillin, amoxicillin, etc.) therapy. These reactions are more likely to occur in individuals with a history of penicillin hypersensitivity. Before initiating therapy with penicillin V, careful inquiry should be made concerning previous hypersensitivity reactions to penicillins or cephalosporins. If subjects have a known hypersensitivity to penicillin/amoxicillin they may be prescribed an alternative antibiotic at the outset.

Other frequently reported adverse effects in patients taking penicillin are diarrhea/loose stools, nausea, skin rashes and urticaria, and vomiting. Patients should, therefore, be advised that these reactions may occur.

8.4.1.3 Alternative prophylactic antibiotics

- Erythromycin 500 mg twice daily
- Azithromycin 500 mg 3 times per week

Erythromycin 500 mg twice daily or Azithromycin 500 mg 3 times per week may be considered as suitable alternatives in subjects who are unable to tolerate penicillin.

The PI will discuss and agree to a suitable alternative with the sponsor's medical monitor. The agreement will be noted in the subject's medical records.

8.4.2 Rescue antibiotics

Body temperature, vital signs and relevant blood parameters will be monitored regularly throughout the study to assess for signs of infection. The PI should be contacted immediately in the event of a suspected infection despite prophylactic antibiotic treatment for guidance and appropriate action to be taken. Action to be taken may include administration of a broad spectrum antibiotic to cover possible resistant organisms such as resistant pneumococcus (e.g. levofloxacin).

8.4.3 Vaccinations

Vaccination against *Neisseria meningitidis* types A, C, W, Y and B, *Streptococcus pneumoniae* and *Haemophilus influenzae* Type B (Hib) is required to participate in this study, either within 2 years prior to Day 1 dosing, or within 14 days after starting treatment with APL-2.

If required i.e. not previously vaccinated subjects will receive vaccinations against *Neisseria meningitidis* types A, C, W, Y and B, *Streptococcus pneumoniae* and *Haemophilus influenzae* Type B (Hib). If the subject's first documented *Neisseria meningitidis* vaccine/s are administered at Day 15, a booster (for both vaccinations) should be administered after 2 months. If Pneumococcal vaccination is required, a dose of PCV13 will be administered at Day 15 and a dose of PPSV23 will be administered at least 8 weeks later (unless documented evidence exists that subjects are non-responders to vaccination as evidenced by titers or display titer levels within acceptable local limits). The PI will discuss with the Sponsor in regard to specific patient requirements

8.4.4 Iron Supplements

For subjects receiving iron supplements at the time of APL-2 initiation, iron supplement doses should be maintained stable throughout the study unless iron levels (ferritin and TIBC) increase to unacceptable levels above ULN during the study. Change in dose of iron supplementation should be discussed with the Sponsor prior to implementation

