7.1 Inclusion Criteria

At Screening (unless otherwise specified), subjects must fulfill all of the following inclusion criteria to be eligible for participation in the study:

1. At least 18 years old (inclusive)
2. Diagnosed with PNH (WBC clone >10%)
3. Lactose dehydrogenase ≥ 2 times the upper limit of normal
4. Screening Ferritin \geq normal and Total Iron Binding Capacity (TIBC) \leq LLN based on central lab reference ranges. If a subject is receiving iron supplements at screening, the investigator must ensure that his/her dose has been stable for 8 weeks prior to enrolment and must be maintained throughout the study (see [Section 8.4.4](#))
5. Last transfusion within 12 months prior to screening
6. Platelet count of $>30,000/\text{mm}^3$ at the screening visit
7. Absolute neutrophil count $>500/\text{mm}^3$ at the screening visit
8. Women of child-bearing potential (WOCBP) must have a negative pregnancy test at screening and must agree to use protocol defined methods of contraception for the duration of the study
9. Males must agree to use protocol defined methods of contraception and agree to refrain from donating sperm for the duration of the study
10. Vaccination against Neisseria meningitides types A, C, W, Y and B, Streptococcus pneumoniae and Haemophilus influenzae Type B (Hib) either within 2 years prior to Day 1 dosing, or within 14 days after starting treatment with APL-2. Unless documented evidence exists that subjects are non-responders to vaccination as evidenced by titers or display titer levels within acceptable local limits
11. Willing and able to give informed consent

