8.4.5 Phlebotomy/Venesection for iron overload

Phlebotomy/Venesection should only be considered if the Hb is within the normal range and may only be initiated if the need and frequency have been discussed and agreed to with the Sponsor.

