10.1.7.3 Serum Chemistry

- Blood urea nitrogen (BUN)
- Creatinine
- Estimated creatinine clearance (using Cockcroft-Gault formula) – screening only
- Bilirubin (total and direct)
- Albumin
- Aspartate aminotransferase (AST)
- ALT
- Uric acid
- Glucose
- Sodium

- Alkaline phosphatase (ALP)
- Lactate dehydrogenase (LD)
- Haptoglobin
- Gamma-glutamyl transpeptidase (GGT)
- Creatine kinase (CK)
- Potassium
- Chloride
- Ferritin
- B12/folate
- Total Iron Binding Capacity (TIBC)

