11. ADVERSE EVENTS

11.1 Definitions

An adverse event (AE) is any untoward medical occurrence associated with the use of a drug in humans, whether or not considered drug related. An AE can therefore be any unfavorable and unintended sign, including a clinically significant abnormal laboratory finding, symptom, or disease temporally associated with the use of a study drug, whether or not considered related to the study drug.

Adverse events include the onset of new illness and the exacerbation of pre-existing conditions. Any medical condition that is present at the time that the subject is screened should be recorded on the medical history eCRF and not reported as an AE. However, if that condition deteriorates or severity changes at any time during the study, it should be recorded as an AE.

Any AEs that occur prior to dosing on Day 1 will be categorized as pre-treatment events. Treatment-emergent adverse events (TEAEs) will be defined as those AEs that occur after dosing on Day 1 and up to 30 days after the last dose of study medication.

A suspected adverse reaction means any AE for which there is a reasonable possibility that the drug caused the AE. Reasonable possibility means there is evidence to suggest a causal relationship between the drug and the AE.

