11.7 Treatment and Follow up of Adverse Events

AEs (whether serious or non-serious), including clinically significant abnormal laboratory test values, will be evaluated by the Investigator and treated and/or followed up until the symptoms or value(s) return to baseline or are clinically stable. Treatment of AEs will be performed by appropriately trained medical personnel, either at the clinical site or at a nearby hospital emergency room. When appropriate, medical tests and/or examinations will be performed to document resolution of the event(s).

AEs continuing after completion of the study will be followed up by telephone or with visits per the discretion of the PI. If possible, the outcome of any AE that caused discontinuation from the study or was present at the end of the study should be reported, particularly if the AE was considered by the PI to be related to the study drug.

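### Protocol Section 8.4.4 counts a rise in TIBC as iron excess, against inclusion criterion 4, so the exception to the iron-dose hold is wrong as written (minor)

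*Protocol*

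**What the plan says.** Three protocol provisions deal with iron.

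- **Section 7.1, criterion 4** (repeated in the synopsis) requires, at screening, ferritin at or above normal and TIBC at or below "LLN based on central lab reference ranges". For a subject on iron supplements, the "dose has been stable for 8 weeks prior to enrolment and must be maintained throughout the study". The only qualifier is a cross-reference to Section 8.4.4.
- **Section 8.4.4** covers subjects on iron when APL-2 starts. Doses should stay stable "unless iron levels (ferritin and TIBC) increase to unacceptable levels above ULN during the study". It adds: "Change in dose of iron supplementation should be discussed with the Sponsor prior to implementation". The level that counts as unacceptable is not defined.
- **Section 8.4.5** covers phlebotomy for iron overload, which "should only be considered if the Hb is within the normal range" and needs Sponsor agreement. It gives no ferritin or TIBC threshold and does not mention supplements.

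Ferritin and TIBC are both in the serum chemistry panel (Section 10.1.7.3). Neither the protocol nor the SAP gives any other rule for changing the iron dose.

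**The concern.** Sections 7.1 and 8.4.4 are linked by cross-reference and use the same two markers, but they treat TIBC in opposite directions. At entry, adequate iron goes with high or normal ferritin and low TIBC. In 8.4.4, too much iron goes with high ferritin and high TIBC. One marker in the exception is therefore reversed relative to the protocol's own eligibility rule.

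What is at stake is safety. The exception lets a site stop or reduce iron in a subject who has too much. A site that applied the words strictly could keep iron fixed in a supplemented subject whose ferritin had risen above ULN, because TIBC had not risen as well.

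**Working it through.** No arithmetic from the plan applies, and there is no stated figure to reproduce. The check is a logical one: take the four possible ferritin and TIBC patterns and ask whether each releases the hold.

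| Ferritin > ULN | TIBC > ULN | Both required | Either suffices | Ferritin rule |
|---|---|---|---|---|
| Yes | Yes | released | released | released |
| Yes | No | **held** | released | released |
| No | Yes | held | **released** | held |
| No | No | held | held | held |

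1. **Both markers required.** Only the first row releases the hold. Compared with a rule based on ferritin, one pattern of four is missed: ferritin above ULN with TIBC low or normal.

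2. **Where subjects start.** Criterion 4 puts every eligible subject at TIBC at or below LLN, so all start in the second or fourth row. Under the joint reading neither row releases the hold. To reach the first row, TIBC must cross its whole reference range, from at or below LLN to above ULN, while ferritin is also above ULN.

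3. **Either marker suffices.** The second row is now covered, but so is the third: TIBC above ULN with ferritin not raised. That counts a TIBC rise alone as iron excess, the reverse of the direction in criterion 4. So this reading does not repair the clause. It replaces one wrong pattern of four with another.

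4. **Whether other text corrects the clause.** Section 8.4.5 concerns phlebotomy only, and only with Hb in the normal range. The Sponsor-discussion sentence in 8.4.4 is a procedure and sets no criterion. Sections 11.1 and 11.7 are general adverse-event provisions with no iron rule. None states a ferritin-only trigger or reverses the direction for TIBC.

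5. **How many subjects.** The clause applies only to subjects on iron at APL-2 initiation. That number is not given. SAP Section 1 says enrollment closed with 4 subjects, so the range is 0 to 4.

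The pattern counts describe the logic of the rule. They say nothing about how often each pattern would occur.

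**The case against.** The strongest reply is that the joint test is not the natural reading. The subject of the clause is iron levels, and the parenthesis may simply name the tests to watch, leaving the clinician to judge what is unacceptable. Nothing in the documents shows that a site would demand both markers. This has force against the joint reading, but the looser reading still lists TIBC as a marker that rises with iron excess.

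The second reply is that other text softens the effect, and this stands. Section 8.4.4 says should. Its sentence on discussing dose changes with the Sponsor is not tied to the ULN clause or to one direction of change. The adverse-event definition takes in untoward signs "including a clinically significant abnormal laboratory finding, symptom, or disease temporally associated with the use of a study drug", and under Section 11.7 such events "will be evaluated by the Investigator and treated and/or followed up until the symptoms or value(s) return to baseline" or are clinically stable. The SAP lists all concomitant medications (5.5) and all laboratory data with out-of-range values flagged (7.2), so a raised ferritin or an iron change would be visible afterwards.

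A reader might also infer that the clause threatens the Hb results, since Hb is a primary efficacy endpoint and there is no control arm. The documents do not support that. The joint reading makes the exception harder to use, so iron stays constant, which helps within-subject comparison of Hb. No Hb bias is shown.

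Nor should a reader infer that the protocol forbids reducing iron in an overloaded subject. The Sponsor route and Section 11.7 leave that open.

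**Conclusion.** The point holds as a minor error of wording with a safety bearing. Section 8.4.4 treats TIBC above ULN as a sign of excess iron, contrary to criterion 4, and neither reading of the parenthesis gives a correct rule. The joint reading misses high ferritin with low or normal TIBC; the either-marker reading admits a TIBC rise alone.

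The size is small. Between 0 and 4 subjects could be affected, and case-by-case routes exist. Analysis is descriptive, with no formal inference (Protocol Section 12.2), and no planned analysis depends on the clause. The clinical consequence cannot be sized from the documents.

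The conclusion assumes that criterion 4 states the intended direction for TIBC. It sets an upper bound on TIBC beside a lower bound on ferritin, so it pairs the markers in opposite directions whatever the exact limits.

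**What to change.** In Section 8.4.4:

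- Base the excess-iron exception on ferritin above ULN, at a limit set by the sponsor's medical team, after discussion with the Sponsor.
- Delete TIBC above ULN as a sign of excess iron.
- Do not substitute TIBC at or below LLN alone as the trigger. Criterion 4 requires it at entry, so every eligible subject would meet it on starting treatment.

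The cost is one or two sentences. No test or visit is added, because both markers are already in the chemistry panel. With enrollment closed, the change is mainly useful for any extension or later protocol that reuses this wording.

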8.4.5 Phlebotomy/Venesection for iron overload

Phlebotomy/Venesection should only be considered if the Hb is within the normal range and may only be initiated if the need and frequency have been discussed and agreed to with the Sponsor.

9. STUDY PROCEDURES

Please see the Study Flow Chart in [Section 2](#) for a summary of the schedule of study participation and procedures. The schedule of visit dates should be established, either, prior to, or at the time of screening allowing subjects an opportunity to assess whether there are likely to be significant conflicts with other activities or planned absences. To the extent possible, subjects will be expected to adhere to the visit schedule and any re-scheduling of visits must be agreed, in advance, with the investigator and sponsor to ensure that the dosing of study medication can continue daily as required.

If a subject's dose is increased beyond 270 mg/day in Part 2B additional site visits will be scheduled for the first 6 weeks of dose increase, alternating with the monthly visits in the protocol.

i.e. subjects will return to the clinical site every two weeks for 6 weeks. These will be scheduled by the investigator and the same procedures as the monthly visits will be performed. These visits will be recorded as unscheduled visits.

9.1 Screening

Screening will begin within 30 days prior to dosing to confirm that subjects meet the subject selection criteria for the study. Informed consent will be obtained at screening (see [Section 13.3.3](#)). Subjects will have to meet all eligibility criteria before being enrolled into the study (see [Section 7](#)).

The following will be recorded at screening: medical history and demographic data, including, sex, age, race, body weight (kg), height (cm).

Screening procedures are listed in the Study Flow Chart in [Section 2](#).

9.2 Part 1 - Treatment Period – (Days 1 to 28)

Subjects will receive daily SC doses of APL-2 on Days 1 to 28. APL-2 will be administered at the clinical site by study personnel during the first 3 days and thereafter by the subject under supervision whilst at the clinical site or off-site self-administered by the subject. Subjects will be trained to prepare and administer their infusions of APL-2, complete the administration diary and injection site assessment.

9.2.1 On Site Administration (Day 1 to Day 3 and Days 8, 15 and 22)

The first 3 daily SC doses of APL-2 (Day 1 to 3) will be administered by study personnel. Doses on 8, 15 and 22 will be administered, by the subject under supervision, at the clinical site. Subjects will remain in the clinic for at least 2.5 hours after receiving the first dose of APL-2 on Day 1.

If required subjects will receive vaccinations on Day 15 with boosters scheduled appropriately. Antibiotic therapy will be changed from ciprofloxacin to penicillin V.

Blood samples for laboratory analysis, PK/PD, and antigenicity will be taken during site visits as outlined in the Study Flow Chart in [Section 2](#).

Specific procedures for each visit are listed in the Study Flow Chart.

9.2.2 Outpatient Administration (Day 4 to Day 28)

From Day 4 to Day 28 daily doses of APL-2 will be self-administered by the subject at home with the exception of Days 8, 15 and 22 (see above).

Subjects will be trained to notify the PI or other study personnel in the event that an injection site reaction occurs after self-administration of APL-2. All clinically significant findings, as determined by the investigator, from injection site or related to pump use will be recorded as AEs.

9.3 Part 2A - Treatment Period – (Days 29 to 84)

Each subject will receive daily SC doses of APL-2 on Days 29 to 84. APL-2 will be administered by the subject. If a clinical benefit is not observed, treatment will stop on Day 28. The subject will skip Part 2A and enter Part 3 for safety follow up visits.

9.3.1 On Site Administration (Days 29, 36, 43, 57 and 71)

Daily SC doses of APL-2 on Days 29, 36, 43, 57 and 71 will be administered at the clinical site by the subject.

Blood samples for laboratory analysis, PK/PD and antigenicity will be taken during site visits as outlined in the Study Flow Chart in [Section 2](#).

Specific procedures for each visit are listed in the Study Flow Chart.

9.3.2 Outpatient Administration (Day 30 to Day 84)

From Day 30 to Day 84 daily doses of APL-2 will be self-administered by the subject at an off-site location convenient to the subject, with the exception of Days 36, 43, 57 and 71 (see above) where the dose will be administered at the clinical site by the subject.

9.4 Part 2B - Treatment Period – (Days 85 to 364)

Each subject will receive daily SC doses of APL-2 on Days 85 to 364. APL-2 will be administered at the site by the subject. If a clinical benefit is not observed, treatment will stop on Day 84. The subject will skip Part 2B and enter Part 3 for safety follow up visits.

9.4.1 On Site Administration (Days 85, 113, 141, 169, 197, 225, 253, 281, 309, and 337)

Daily SC doses of APL-2 on Days 85, 113, 141, 169, 197, 225, 253, 281, 309, and 337 will be administered at the clinical site by the subject.

Blood samples for laboratory analysis, PK/PD and antigenicity will be taken during site visits as outlined in the Study Flow Chart in [Section 2](#).

Specific procedures for each visit are listed in the Study Flow Chart.

